5 STUDY DESIGN

5.1 Overall Design

This is a Phase 1/2, open-label study of BMS-986249 administered as a single agent and in combination with nivolumab in participants with advanced solid tumors. The study is composed of 2 parts: dose escalation and dose expansion.

Part 1: The Dose Escalation Phase is where the dose of BMS-986249 will be given alone (Part 1A) or in combination with nivolumab (Part 1B). The Part 1A monotherapy dose escalation will evaluate different doses of BMS-986249 starting at 240 mg followed by 800, 1,600, and 2,400 mg (flat doses, Q4W). If during the monotherapy Dose Escalation Phase (Part 1A) it appears that a dose is associated with an unacceptable frequency of toxicities, then a conditional dose (eg, intermediate dose or alternative administration schedule [eg, Q8W, see Appendix 12]) may be evaluated in the study after clinical evaluation of the available safety, PK, and data. Alternative dose schedules will be initiated and documented by a note to file or administrative letter following discussions and agreement between the investigators and Medical Monitor (or designee).

The BMS-986249 Monotherapy Dose Escalation (Part 1A) will escalate the dose of BMS-986249 to determine a safe and efficacious dose. The study will first evaluate the safety and tolerability of monotherapy BMS-986249 Q4W, based on DLTs using a Bayesian Logistic Regression Model (BLRM) employing the escalation with overdose control (EWOC) principle.

The Safety Evaluation of Combination Doses of BMS-986249 with Nivolumab (Part 1B) will evaluate the safety and tolerability of doses of BMS-986249 in combination with nivolumab. Part 1B will begin only when data (safety and PK) on BMS-986429 at 240 mg (equivalent to approximately 3 mg/kg) and 800 mg (equivalent to approximately 10 mg/kg) are available from the monotherapy dose-escalation cohort (Part 1A). In Part 1B, the dose of BMS-986429 will be escalated, whereas the dose of nivolumab will be fixed at 480 mg Q4W. However, if an MTD is identified, then additional cohorts with lower doses of nivolumab and then potential higher doses of BMS-986249 may be studied as outlined in the study schematic (Figure 5.1-1). Alternative administration schedules of BMS-986249 (eg, Q8W, see Appendix 12 and Figure 5.1-1) may also be explored after clinical evaluation of available safety, PK, and data. Alternative dose schedules will be initiated and documented by a note to file or administrative letter following discussions and agreement between the investigators and Medical Monitor (or designee).

To better estimate the preliminary safety profile and PK of any cohort in Part 1A or 1B, additional participants may be enrolled to cohorts deemed tolerable per the BLRM method.

Part 2: The BMS-986249 Cohort Expansion Combination Therapy Phase will open upon an overall assessment of available preliminary safety, PK, and data from Part 1A and Part 1B. The different dose levels selected for Part 2 will not exceed the highest dose level assessed and deemed tolerable in Part 1. Part 2 will expand a specific patient population to assess the anti-tumor activity, safety, and tolerability of BMS-986249 in combination with nivolumab. PK,

, and patient-reported outcome (PRO) information of BMS-986249 in combination with nivolumab will also be evaluated.

The BMS-986249 in Combination with Nivolumab Randomized Cohort Expansion in Melanoma (Part 2A) will include participants with previously untreated, unresectable or metastatic melanoma. Part 2A participants will be stratified by PD-L1 status (≥ 1% tumor cell surface expression versus < 1% tumor cell expression/indeterminate) and American Joint Committee on Cancer Version 7 (AJCC) M-stage (M0/M1a/M1b versus M1c), and initially randomized 1:1:1:1:1 between 5 treatment arms:

- Arm A: 240 mg BMS-986249 in combination with 360 mg nivolumab administered IV Q3W for 4 doses (Combination Therapy Phase) as a co-administration, followed by 480 mg nivolumab monotherapy administered IV over approximately 30 minutes Q4W (Maintenance Phase), which will begin 3 weeks after the last combination dose.
- Arm B: 800 mg BMS-986249 administered IV Q8W in combination with 480 mg nivolumab administered IV Q4W. Co-administration will continue on cycles where both study treatments are scheduled, while nivolumab will be administered IV over approximately 30 minutes when scheduled as a monotherapy.
- Arm C: 1,200 mg BMS-986249 administered IV Q8W in combination with 480 mg nivolumab administered IV Q4W. Co-administration will continue on cycles where both study treatments are scheduled, while nivolumab will be administered IV over approximately 30 minutes when scheduled as a monotherapy.
- Arm D: 3 mg/kg ipilimumab in combination with 1 mg/kg nivolumab administered IV Q3W for 4 doses (Combination Therapy Phase), followed by 480 mg nivolumab monotherapy administered IV over approximately 30 minutes Q4W (Maintenance Phase), which will begin 3 weeks after the last combination dose. Nivolumab and ipilimumab will be administered sequentially as 2 separate IV infusions. Nivolumab will be given first, over approximately 30 minutes, followed by ipilimumab over approximately 30 minutes, beginning approximately 30 minutes after completion of the infusion of nivolumab.
- Arm E: 480 mg nivolumab monotherapy administered IV over approximately 30 minutes Q4W.
- Addendum Per Revised Protocol 07: Part 2A Arm A, Arm B, and Arm E are discontinued for further enrollment/randomization. The modification of enrollment/randomization in Part 2A is not a consequence of changes in the safety or tolerability profile or benefit/risk assessment of BMS-986249 (see Section 5.5.4). Currently active participants in these arms will continue treatment as assigned and may remain on treatment until protocol-defined discontinuation criteria have been met. In accordance with Revised Protocol 07, participants in Part 2A will be randomized across the study approximately 1:1:1 between 3 treatment arms:
 - Arm C: described above
 - Arm D: described above
 - Arm F: 600 mg BMS-986249 administered IV Q4W in combination with 480 mg nivolumab administered IV Q4W as a co-administration.

The BMS-986249 in Combination with Nivolumab Additional Tumor Cohort Expansion (Part 2B) will be comprised of signal seeking expansion cohorts including advanced or intermediate HCC participants previously treated with prior anti-PD-(L)1 therapy (Cohort 1), metastatic castration-resistant prostate cancer (mCRPC) participants treated with a prior taxane-containing chemotherapy regimen (Cohort 2), and unresectable locally advanced or metastatic TNBC participants treated with a prior chemotherapy-based treatment (Cohort 3). In each Part 2B single-arm tumor-specific expansion cohort, participants will receive 1,200 mg BMS-986249 administered IV Q8W in combination with 480 mg nivolumab administered IV Q4W. Co-administration will continue on cycles where both study treatments are scheduled, while nivolumab will be administered IV over approximately 30 minutes when scheduled as a monotherapy. The duration of study participation will be approximately 4 years (treatment of up to 2 years and follow-up of up to 2 years).

Addendum per Protocol Amendment 09: The duration of study participation will be approximately 2 years and 3 months (treatment of up to 2 years and Follow-up Period of 100 days post EOT).

At the Sponsor's discretion, scans will be submitted to an imaging core laboratory and may be reviewed by blinded independent central review (BICR) at a later date or at any time during the study.

The study design schematic is presented in Figure 5.1-1 (Part 1) and Figure 5.1-2 (Part 2). A detailed schematic for study-period and participant flow is presented in Figure 5.1-3.

[figure not shown]
[figure not shown]

Figure 5.1-1: Study Design Schematic - Part 1, the Dose Escalation Phase

Abbreviations: BMS = Bristol Myers Squibb; CRC = colorectal cancer; CRPC = castration-resistant prostate cancer; CTLA-4 = cytotoxic T lymphocyte-associated protein 4; DLT = dose-limiting toxicity; NSCLC = non-small cell lung cancer; PD-1 = programmed cell death protein 1; PD-L1 = programmed death ligand-1; Q4W = every 4 weeks; Q8W = every 8 weeks; RCC = renal cell carcinoma; SCLC = small cell lung cancer.

- ^a Alternative dosing schedules (eg, Q8W) may occur after evaluation of available safety, PK, and data, and upon discussion and agreement between the investigators and Medical Monitor (or designee), refer to Appendix 12.
- b Participants in the monotherapy arm must be anti-CTLA-4-naive. Prior anti-PD-1 or anti-PD-L1 exposure is allowed in the monotherapy arm, but at time of enrollment, participants must be at least 5 half-lives (approximately 100 days) from last dose of PD-1/PD-L1 therapy.
- ^c Intra-participant dose escalation/reduction of BMS-986249 or nivolumab is not permitted.
- d Part 1B will not start until demonstration of acceptable safety in at least 2 cohorts from Part 1A has occurred. Subsequently, treatment in both parts will occur in parallel.
- ^e Part 1B participants with NSCLC will only be evaluated in a cohort once the DLT evaluation for that cohort has been completed.

Figure 5.1-2: Study Design Schematic - Part 2, the BMS-986249 Cohort Expansion Combination Therapy Phase

Abbreviations: AJCC = American Joint Committee on Cancer; CRPC = castration-resistant prostate cancer; HCC = hepatocellular carcinoma; IV = intravenous; PD-L1 = programmed death ligand-1; Q3W = every 3 weeks; Q4W = every 4 weeks; Q8W = every 8 weeks; TNBC = triple-negative breast cancer.

^a Will only open upon evaluation of available data from Parts 1A and 1B.

Per Revised Protocol 07, Part 2A Arm A, Arm B, and Arm E were closed to enrollment and are not displayed. Part 2A Arm A, 240 mg BMS-986249 IV Q3W in combination with 360 mg nivolumab IV Q3W for 4 doses followed by nivolumab monotherapy Maintenance Phase of 480 mg nivolumab IV Q4W continuous. Part 2A Arm B, 800 mg BMS-986249 IV Q8W in combination with 480 mg nivolumab IV Q4W continuous. Part 2A Arm E, 480 mg nivolumab IV Q4W continuous.

Treatment Period On treatment fresh biopsy during this time Parts 1A and 1B: 4-week cycles for up to 2 years Follow-up Safety: Visits on Day 30, 60, and 100 (\pm 7 days) after EOT Part 2A: For up to 2 years Arm C: 4-week cycles of 1200 mg BMS-986249 administered Q8W + 480 mg nivolumab Imaging: Part 1: Q12W (±7 days) after study treatment administered Q4W discontinuation^c Screening Arm D: Four 3-week cycles of 3 mg/kg ipilimumab + Part 2A: 12 weeks (± 7 days) from first dose, EOT 30 days 1 mg/kg nivolumab, followed by 4-week then Q8W (± 7 days) until 52 weeks, Fresh biopsy^a cycles of 480 mg nivolumab monotherapy and Q12W (± 7 days) thereafter starting 3 weeks after last combination dose Part 2B: Q8W (± 7 days) from first dose up until Arm F: 4-week cycles of 600 mg BMS-986249 + 48 weeks, and Q12W (\pm 7 days) 480 mg nivolumab Part 2B: 4-week cycles of 1200 mg BMS-986249 administered Survival: EOT + 2 years

Figure 5.1-3: Study Period and Participant Flow

Q8W + 480 mg nivolumab administered Q4W for up

Abbreviations: BMS = Bristol Myers Squibb; EOT = end of treatment, Q4W = every 4 weeks; Q8W = every 8 weeks; Q12W = every 12 weeks.

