Variable: Treatment Related AE with CTCAE Grade 3 or higher that occurred within 24 weeks from first dose Intercurrent events: early discontinuation of study

Treatment Policy: Patients that discontinue treatment early will have a 100 days post last dose safety follow-up. AEs occurring after this safety follow-up window will not be included in the analysis, even if they occurred within the 24 weeks from first dose.

Intercurrent event: initiation of subsequent anti-cancer therapy

While on treatment: Patients that initiate an anti-cancer subsequent therapy will be discontinued from study but will be followed up for safety events 100 days from last dose. Safety events regardless of whether they occur before or after subsequent therapy will be include in the analysis. AEs occurring past 100 days safety follow-up will not be included in the analysis, even if they occurred within the 24 weeks from first dose.

Intercurrent event: death and withdrew

While on treatment: Patients who die or withdraw consent before reaching the 24 weeks landmark will be included in the analysis and their Grade 3 to 5 treatment related AEs will be include in the summary.

Population level summary: Grade 3 to 5 treatment related adverse event incidence rate, comparison of Arm C vs Arm D and Arm F vs Arm D with estimated difference and odd ratio and 80% confidence interval using Cochran Mantel Haenszel methodology adjusting for stratification factors will be computed. Adjusted and unadjusted chi square test will be performed and p-values will be provided.

Objective	Endpoint
Primary	Primary
To evaluate the preliminary efficacy of BMS-986249 in combination with nivolumab (Arm C and Arm F) relative to historic nivolumab monotherapy data in participants with previously untreated, unresectable or metastatic melanoma	ORR as assessed by investigator using RECIST v1.1

Main Estimand for the Primary Objective

Treatment: 1200 mg BMS-986249 IV Q8W + 480 mg nivolumab IV Q4W (Arm C); 3 mg/kg ipilimumab Q3W + 1 mg/kg nivolumab IV Q3W for 4 doses followed three weeks later by 480 mg nivolumab IV Q4W(Arm D); 600 mg BMS-986249 IV Q4W + 480 mg nivolumab IV Q4W (Arm F)

Population: All treated participants with evaluable baseline tumor assessment per RECIST v1.1

Variable: BOR, defined as the best response, as determined by investigator, per RECIST 1.1

Intercurrent events: early discontinuation of study

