5.2 Number of Participants

- Part 1A Monotherapy Escalation: The total sample size is up to approximately 45 evaluable participants.
- Part 1B Combination Escalation: The total sample size is up to approximately 60 evaluable participants.
- Part 2A Expansion in Melanoma: The total sample size is up to approximately 200 evaluable participants with approximately 60 evaluable participants each treated in Arm C, Arm D, and Arm F, respectively. Prior to Revised Protocol 07, up to approximately 20 evaluable participants may have been enrolled across Arms A, B, and E, collectively. (See Section 10.1.2.)
- Part 2B Additional Tumor Cohort Expansion: The total sample size is up to approximately 120 evaluable participants with approximately 40 evaluable participants per tumor type cohort.

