7.2 Method of Treatment Assignment

Participants will be enrolled using an Interactive Response Technology (IRT) system; until this system is activated, enrollment will be manually managed by the Sponsor.

During dose escalation, all participants will be assigned to Part 1A until the decision is made to escalate to the third dose cohort. Subsequently, treatment in Part 1B will be initiated, and dose escalation in the 2 parts will occur in parallel. Treatment assignments for participants eligible for both Part 1A and Part 1B will prioritize Part 1B through IRT whenever possible. If there are no openings in Part 1B, then the participant will be assigned to the next open part/cohort. Prioritization of participants eligible for both Part 1A and Part 1B may be modified to ensure the dose of Part 1B does not exceed the highest tolerated dose in Part 1A. If Part 1 is open upon the decision to initiate Part 2, treatment in the 2 parts will occur in parallel. Treatment assignments for participants eligible for Part 1A or Part 1B, and Part 2 will prioritize Part 2 through IRT whenever possible. If there are no openings in Part 2, then the participant will be assigned to the next open part/cohort.

In the BMS-986249 in Combination with Nivolumab Randomized Cohort Expansion in Melanoma (Part 2A) every participant that signs the informed consent form will be assigned a participant identification number in IRT. In order to be randomized, pre-treatment tumor tissue obtained in the metastatic setting or from an unresectable site of disease must be provided for biomarker analyses. A participant must have quantifiable PD-L1 expression (≥ 1% or < 1% tumor cell membrane staining) or be classified as PD-L1 indeterminate. Participants will be stratified by PD-L1 expression and M-stage. Participants meeting eligibility criteria were to be randomized in a 1:1:1:1:1 ratio to Arms A - E. As of Revised Protocol 07, further enrollment/randomization into Part 2A Arms A, B, and E is closed, and Arm F is added. Across study randomization for Part 2A participants meeting eligibility criteria will randomize in approximately a 1:1:1 ratio to open arms (eg, Part 2A Arms C, D, and F). If there is a change to randomization (eg, discontinuation of an

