The final analysis will take place when all randomized participants have completed at least 36 weeks follow-up or discontinue earlier. Due to exploratory nature of the proof of concept (PoC) design, no multiplicity adjustment will be made for testing multiple endpoints or multiple treatment arms.

10.1.2.2 Changes to Sample Size Assumptions for Revised Protocol 07

[figure not shown]
The original sample size calculation was based on a 60% two-sided CI of ORR for the difference between treatments and required 54 participants per arm. As participants in Arm E will not be randomized as originally planned, the efficacy evaluation and the statistical comparison will use a reference value of based on nivolumab monotherapy historical data in melanoma (see Section 5.4.7.2).

One of the main objectives of this study is to evaluate the preliminary safety and tolerability of BMS-986249 in combination with nivolumab (Part 2A Arm C and Arm F).

Based on final analysis of CA209511, the ipilimimab 3 mg/kg in combination with nivolumab 1 mg/kg, the incidence rate of drug-related Grade 3-5 AEs within 24 weeks is estimated to be relative improvement in the incidence of Grade 3-5 TRAEs is considered to be clinically relevant.

Using a two group $\chi 2$ test with a 0.10 one-sided significance alpha level, assuming a 1:1 randomization ratio of experimental BMS-986249 in combination with nivolumab containing regimen to control ipilimumab in combination with nivolumab, a sample size of 60 participants per arm will have approximately 70% power to detect a ratio in favor of the alternative hypothesis of compared to the null hypothesis proportion of

The null hypothesis is the ratio of proportions above or equal to 1, the alternative hypothesis is the ratio of proportion is below to 1.

Protocol Amendment No.: 09 Date: 14-Mar-2023

e: 14-Mar-2023

The final analysis will take place when all randomized participants have completed at least 36 weeks follow-up or discontinue earlier. Due to exploratory nature of the PoC design, no multiplicity adjustment will be made for testing multiple endpoints or multiple treatment arms.

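### The primary Arm F vs Arm D safety comparison pools in Arm D participants randomised before Arm F existed; the effect is modest and the repair is cheap

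*Combined protocol and SAP*

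**What the plan says.** - **Allocation.** Section 5.1 describes an initial 1:1:1:1:1 randomisation to Arms A to E, stratified by PD-L1 status and AJCC M-stage. Section 7.2 then states: "As of Revised Protocol 07, further enrollment/randomization into Part 2A Arms A, B, and E is closed, and Arm F is added". From that point "participants in Part 2A will be randomized across the study approximately 1:1:1 between 3 treatment arms" (Section 5.1). Arms C and D therefore recruited in both periods and Arm F only in the second.
- **Numbers.** Section 5.2 plans "approximately 60 evaluable participants each treated in Arm C, Arm D, and Arm F, respectively" and adds: "Prior to Revised Protocol 07, up to approximately 20 evaluable participants may have been enrolled across Arms A, B, and E, collectively". It gives no count of early participants in C or D.
- **Primary safety analysis.** In Table 4-4 the population is all treated participants, and the named contrasts are C vs D and F vs D. The difference and odds ratio, with an 80% interval, "using Cochran Mantel Haenszel methodology adjusting for stratification factors will be computed". Adjusted and unadjusted chi-square tests are also planned. The stratification factors are PD-L1 and M-stage (Section 5.4.8).
- **Early participants.** Section 10.3.1 makes the pre-07 data from Arms A, B and E descriptive only. It says nothing about early Arm D participants.
- **Status of the SAP.** Section 10.3 calls its text a summary and says a SAP will be finalised before database lock. No separate SAP text is available to review.

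**The concern.** An Arm D participant randomised before Revised Protocol 07 had no chance of being assigned to Arm F. Using that participant as a control for Arm F is a comparison across time, placed inside an analysis presented as randomised. Anything that changed between the two periods and affects the rate of treatment-related Grade 3-5 events enters the F vs D estimate, and stratifying on PD-L1 and M-stage does not remove it.

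The protocol gives reasons to take this seriously. Section 5.4.7 justifies concurrent reference arms because historical controls may no longer represent current patients. Section 5.4.7.2 closes Arm E partly because of the evolving melanoma treatment landscape. Appendix 15 records eligibility changes at Revised Protocol 07 (leptomeningeal metastasis and HIV criteria) and at Amendment 08 (prior adjuvant melanoma therapy). The study is open-label, and relatedness is judged by the investigator (Appendix 3).

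At stake is the validity of one of the two primary safety contrasts.

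**Working it through.** **1. The plan's own figure.** Section 10.1.2.2 uses a two-group chi-square test "with a 0.10 one-sided significance alpha level, assuming a 1:1 randomization ratio of experimental" to control, and says "a sample size of 60 participants per arm will have approximately 70% power to detect a ratio in favor of the alternative hypothesis". The rates are blanked, so the 70% cannot be reproduced exactly. I assume a control rate of 0.55, anchored on the 55.0% Grade 3-4 rate for the combination in Table 5.4.7.1-1 (not limited to 24 weeks), and solve for the experimental rate that gives 70% power. This is 0.386, a ratio of 0.70.

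- Difference: 0.550 − 0.386 = 0.164. Pooled rate: 0.468.
- Null SE: √(2 × 0.468 × 0.532 / 60) = 0.0911; × 1.2816 = 0.1168.
- Alternative SE: √((0.55 × 0.45 + 0.386 × 0.614) / 60) = 0.0899.
- Power: Φ((0.164 − 0.1168) / 0.0899) = Φ(0.53) ≈ 0.70.

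Assumed control rates of 0.40 to 0.60 give 70% power at ratios of 0.62 to 0.73, so the stated design is coherent.

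**2. How many early Arm D participants?** Section 5.2 balances as 3 × 60 + 20 = 200. This leaves no separate allowance for early C and D participants, so they fall within the 60s. Under 1:1:1:1:1, the expected early count in Arm D is one third of the A + B + E total:

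| A + B + E | Early Arm D | Share of 60 |
|---|---|---|
| 10 | 3.3 | 5.6% |
| 20 (stated ceiling) | 6.7 | 11.1% |

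The figure of 7 used below is the ceiling case rounded up (7/60 = 11.7%). It is an expected value, and chance imbalance could move it slightly.

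**3. Bias.** Bias = (early count / 60) × (early minus later Arm D event rate). The drift is assumed; the documents give none.

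| Assumed drift | 3 early | 7 early |
|---|---|---|
| 10 points | 0.5 | 1.2 |
| 20 points | 1.0 | 2.3 |

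**4. Scale.** With assumed rates of 0.55 and 0.39, the 80% half-width is 1.2816 × √(0.55 × 0.45/60 + 0.39 × 0.61/60) = 1.2816 × 0.0899 = 0.115, or 11.5 points.

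**5. One-sided type I error, 7 early (normal approximation).** If early Arm D toxicity was higher by 10 or 20 points, the nominal 0.10 becomes 0.124 or 0.152. If it was lower by the same amounts, it becomes 0.079 or 0.061. The first direction favours Arm F.

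**6. Cost of using concurrent controls only (60 vs 53).**

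- SE ratio: √((1/60 + 1/53) / (2/60)) = 1.03.
- Power at 0.55 vs 0.386: 68.0%, down from 70.0%. The result is the same to within 0.1 point for control rates of 0.45 to 0.60.

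**The case against.** The strongest reply is that pooling may be the more accurate choice. Dropping 7 Arm D participants adds variance of 0.2475 × (1/53 − 1/60) = 0.000545. The squared bias from pooling is (7/60 × drift)², which reaches that value at a drift of 0.20. Below 20 points of drift, pooling has the smaller mean squared error. The arithmetic is right. It shows that the gain from restriction is modest and that the pooled result deserves to be reported. It does not make the pooled contrast randomised.

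The drift is also hypothetical. The general toxicity algorithms in Appendix 9 are dated 25-Jun-2019, before Revised Protocol 06 (05-Aug-2019) set the Arm A to C doses. Amendment 09 describes its AE-collection wording as already implicit in prior versions. Eligibility did change, but nothing shows an effect of 10 to 20 points on toxicity. The design is an exploratory proof of concept with no multiplicity adjustment. All this limits the size of the problem without removing it.

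A period term could still appear in the SAP. However, Table 4-4 already fixes the population, the contrast and the adjustment.

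A reader might also infer more than the documents support:

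- **That F vs C is affected.** No F vs C test is planned; Table 4-4 names only C vs D and F vs D.
- **That Arm F must be over-allocated after Revised Protocol 07.** This is one reading of the Section 5.1 wording. Section 7.2 can be read as approximately 1:1:1 among the open arms from then on. Pooling occurs under either reading.
- **That the primary ORR objective is compromised.** Its comparator is historical nivolumab data, and the ORR odds ratio in Table 4-4 names no pair of arms.
- **That a CMH period stratum is as good as restriction.** It gives early Arm D participants no weight in F vs D, but the unadjusted chi-square test stays pooled.

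**Conclusion.** The point holds for F vs D on the primary safety endpoint. Followed as written, Table 4-4 and Section 10.3.1 place non-concurrent Arm D participants in a primary contrast without any adjustment for period. C vs D is little affected, because both arms were open in both periods and early Arm D participants have concurrent Arm C controls.

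The size is modest: at most about 7 of 60 Arm D participants, and a bias of about 0.5 to 2.3 points for an assumed drift of 10 to 20 points. This rests on three assumptions: the early count follows the 1:1:1:1:1 ratio from a stated ceiling, the blanked event rates are near those assumed, and the drift is as supposed. Pooling itself is inferred from the all-treated population and the absence of any exclusion; it is not stated outright.

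I rate this a cheap improvement, with medium confidence.

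**What to change.** In Table 4-4 and Section 10.3, and in the SAP when it is written:

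1. Define the F vs D safety comparison, both the CMH analysis and the unadjusted chi-square test, on participants randomised after Arm F opened.
2. Apply the same rule to any F vs D ORR odds ratio that is produced.
3. Report how many Arm D participants were randomised before Arm F opened.
4. Show the all-Arm-D analysis of F vs D as a sensitivity analysis.
5. Keep all participants for C vs D.

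The cost is a change of wording in the protocol and SAP, a fall in F vs D power from about 70% to about 68%, and a standard error about 3% wider. No new data are needed. Restoring 60 concurrent controls would take about 7 more Arm D participants, which the size of the problem does not justify.
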